Definitions: 17-OHP=17-hydroxyprogesterone; ACTH=adrenocorticotropic hormone; AE=adverse event; C-SSRS=Columbia-Suicide Severity Rating Scale; ECG=electrocardiogram; HBsAg=hepatitis B surface antigen; HCV-Ab=hepatitis C virus antibody; HIV-Ab=human immunodeficiency virus antibody; PD=pharmacodynamic; PK=pharmacokinetic; s=serum; u=urine; UDS=urine drug screen. Footnotes are on the following page.

- ^a Final study visit for subjects who complete the study (or early termination). The final study visit will be conducted approximately 3 weeks (+7 days) after the last dose of study drug.
- ^b Day 1 occurs 1 week after the Day -7 visit. Day 1 assessments will be collected predose unless otherwise noted below. Safety assessments collected predose on Day 1 will serve as the baseline.
- ^c Vital signs will be collected on Days 2 and 15 between 8 and 10 and 22 and 24 hours post-evening dose (ie, morning and evening).
- ^d A standard 12-lead ECG will be conducted in triplicate (1 to 3 minutes apart) after subject has rested supine for at least 5 minutes at screening, pre-evening dose on Days 1 and 14, prior to visit completion or discharge on Days 2 and 15, and at the final study visit (Day 35 or early termination).
- e Pregnancy tests will be conducted for female subjects of childbearing potential. A serum pregnancy test will be conducted at screening, and urine pregnancy tests will be conducted at other timepoints. The pregnancy test will be conducted prior to dosing on Day 1 (for eligibility).
- f Includes hematology, clinical chemistry (including creatine kinase, myoglobin, total and conjugated bilirubin), and urinalysis (including quantitative myoglobin, casts and crystals). Samples will be obtained under nonfasted conditions.
- h Urine testing kits will be provided by the central laboratory to confirm negative drug screen prior to Day -7 PD collection and Day 1 dosing. Separate urine sample will also be sent to the central laboratory for analysis.
- ¹ Blood samples for analyses of 17-OHP, androstenedione, testosterone, cortisol, and ACTH will be collected at the following times:
- Screening (between 0700 and 1000 hours; must be collected prior to first morning dose of hydrocortisone).
- Day -7 to Day -6 (24-hour PD baseline): at approximately 1845, 2000, 2300, 0100, 0300, 0700, 1000, 1500, and 1900 hours.
- Days 1 and 14: 15 minutes pre-evening dose and at 1, 4, and 6 hours post-evening dose (±5 minute window).

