- Days 2 and 15: 8, 12, 15, 20, and 24 hours post-evening dose (±15 minute window). The subjects' usual morning dose of concurrent steroidal treatments, study drug dosing, and breakfast (snacks will be allowed prior to breakfast) will be delayed until after the 15 hour postdose PD samples are collected (ie, at approximately 1000 hours) on Day 2. The subjects' usual morning dose of concurrent steroidal treatments will be administered after the 15 hour postdose samples are collected (ie, at approximately 1000 hours) on Day 15.
- Day 7: 12 hours (±2 hour window) after the Day 6 evening dose and prior to the Day 7 morning dose (study drug dosing should not occur until after the blood sample has been collected).
- Day 21: 168 hours (-8 hours/+3 days) following last dose.
- ^k Pharmacokinetic plasma samples will be collected at the following times:
- Days 1 and 14: 15 minutes pre-evening dose and at 1, 4, and 6 hours post-evening dose (±5 minute window).
- Days 2 and 15: 8, 12, and 24 hours post-evening dose (±15 minute window; 24-hour post-evening dose blood sample on Day 15 only).
- Day 7: 12 hours (±2 hour window) after the Day 6 evening dose, prior to the Day 7 morning dose (study drug dosing should not occur until after the blood sample has been collected).
- Days 17 and 21: 72 hours (-8 hours/+3 days) and 168 hours (-8 hours/+3 days) post-final dose.
- Final study visit (+7 days; Day 35 or early termination).
- ¹ The first dose of study drug will be administered at approximately 1900 hours with subjects' evening meal on Day 1. Study drug will be administered at the study center on Days 2 and 14 with subjects' breakfast and evening meals, respectively. The subjects' usual morning dose of concurrent steroidal treatments, study drug dosing, and breakfast (snacks will be allowed prior to breakfast) will be delayed until after the 15-hour postdose PD samples are collected (ie, at approximately 1000 hours) on Day 2. Study drug will be self-administered at home under parent/guardian supervision at approximately 0700 hours (with breakfast) and 1900 hours (with evening meal) on Days 3 to 13.

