- m Subject study diary will be provided to subjects on Day 1 prior to dosing. The date and time of study drug administration, the number of capsules taken, and confirmation that study drug was taken with breakfast and the evening meal will be documented each day. The diary will be reviewed for completeness at the Day 7 visit. The subject will return the diary at the Day 14 visit.
- ⁿ A compliance check will be performed by counting the number of capsules returned.
- ^o Sites should call subjects between the Day 2 and Day 7 visits to remind them to complete the subject study diary, check on compliance, and remind them to bring subject study diary and remaining study drug to the Day 7 visit.
- P Subjects will have the option of having the Days 17 and 21 assessments conducted at home by a qualified home healthcare provider or at the study center.

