8.7.2. Day -7 to Day -6: 24-Hour Baseline Pharmacodynamics

Subjects who continue to meet eligibility requirements will return to the study center for a 24-hour in-patient stay, during which blood samples will be collected for PD analysis. Subjects will not take their usual morning dose of steroidal treatment until after the 1000 hours PD sample is collected on Day -6.

The following study evaluations and tasks will be performed on Day -7 to Day -6:

- Update inclusion/exclusion criteria and medical history.
- Collect vital signs.
- Perform a urine pregnancy test (β -hCG) for female subjects of childbearing potential.
- Collect urine for drug screen and perform alcohol breath test. Urine testing kits will be provided by the central laboratory to confirm negative drug screen prior to PD collection. A separate urine sample will also be sent to the central laboratory for analysis.
- Collect blood samples for PD biomarkers at approximately 1845, 2000, 2300, 0100, 0300, 0700, 1000, 1500, and 1900 hours.
- AE monitoring.
- Record prior and concomitant medications.

Eligible subjects will be instructed to return to the study center on Day 1.

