The subjects' usual morning dose of concurrent steroidal treatments, study drug dosing, and breakfast (snacks will be allowed prior to breakfast) will be delayed until after the 15 hour postdose PD samples are collected (ie, at approximately 1000 hours).

The following study evaluations and tasks will be performed on Day 2:

- Perform a physical examination.
- Collect vital signs between 8 and 10 and 22 and 24 hours post-evening dose (ie, morning and evening).
- Perform 12-lead ECG in triplicate (1 to 3 minutes apart) predose.
- Collect blood samples for PD biomarkers at 8, 12, 15, 20, and 24 hours post-evening dose (±15 minute window).
- Collect blood samples for PK at 8 and 12 hours post-evening dose (±15 minute window).
- •
- AE monitoring.
- Record concomitant medications.

The following procedures will be conducted *before* subjects may be discharged from the study center:

- At approximately 1900 hours, each subject will receive study drug with their evening meal as described in Section 9.3.
- Instruct male subjects and female subjects of childbearing potential who do not practice total abstinence to continue using contraception.
- Instruct subjects to notify the investigator or study staff by telephone if they experience any AEs and before taking any concomitant medications.
- Instruct subjects to continue taking study drug with breakfast (approximately 0700 hours) and with their evening meal (approximately 1900 hours) through Day 13 as described in Section 9.3, and to document in the diary the date and time of study drug administration, the number of capsules taken, and confirmation that study drug was taken with breakfast and the evening meal each day.
- Instruct subjects to bring the subject study diary as well as the remaining study drug back for the Day 7 visit.

Sites should call subjects between the Day 2 and Day 7 visits to remind them to complete the subject study diary, check on compliance, and remind them to bring subject study diary and remaining study drug to the Day 7 visit.

8.7.3.2. Day 7

The following procedures will be performed at the study center on Day 7:

- Perform a physical examination.
- Collect vital signs.
- Perform a urine pregnancy test (β-hCG) for female subjects of childbearing potential.
- Collect blood samples for PD biomarkers at approximately 12 hours (±2 hour window) after the Day 6 evening dose and prior to the Day 7 morning dose.

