The subjects' usual morning dose of concurrent steroidal treatments will be administered after the 15 hour postdose PD samples are collected (ie, at approximately 1000 hours) on Day 15.

The following procedures will be performed on Day 15:

- Perform a physical examination including weight.
- Collect vital signs between 8 and 10 and 22 and 24 hours post-evening dose (ie, morning and evening).
- Perform 12-lead ECG in triplicate (1 to 3 minutes apart).
- Perform a urine pregnancy test (β-hCG) for female subjects of childbearing potential.
- Collect blood sample for clinical laboratory and parameters.
- Collect urine sample for urinalysis.
- Collect blood samples for PD biomarkers at 8, 12, 15, 20, and 24 hours post-evening dose (±15 minute window).
- Collect blood samples for PK at 8, 12, and 24 hours post-evening dose (±15 minute window).
- •
- Administer the C-SSRS (Children's Since Last Visit version).
- AE monitoring.
- Record concomitant medications.

The following procedures will be conducted before subjects may be discharged from the study center:

- Instruct male subjects and female subjects of childbearing potential who do not practice total abstinence to continue using contraception.
- Instruct subjects to notify the investigator or study staff by telephone if they experience any AEs and before taking any concomitant medications.
- Confirm if the subject prefers to have the Days 17 and 21 visits conducted at home instead of at the study center.
 - If the subject elects to have a home visit, instruct him/her that the qualified home healthcare provider will contact him/her to schedule the visit.
 - If the subject elects to come into the study center, instruct him/her to return on Days 17 and 21.

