8.7.4.2. Final Study Visit: (Day 35 or Early Termination)

Subjects will return to the study center for the final study visit (Day 35 or early termination [+7 days]).

The following procedures will be conducted at the final study visit:

• Perform a physical examination including height and weight.

- Collect vital signs.
- Perform 12-lead ECG in triplicate (1 to 3 minutes apart).
- Perform a urine pregnancy test (β-hCG) for female subjects of childbearing potential.
- Collect blood sample for clinical laboratory parameters.
- Collect urine sample for urinalysis.
- Collect blood sample for PK.
- Administer the C-SSRS (Children's Since Last Visit version).
- AE monitoring.
- Record concomitant medications.

8.8. **Study Duration**

The expected duration of study participation for each subject is approximately 9 weeks, including up to approximately 3 weeks for screening, a 24-hour PD baseline period (approximately 7 days prior to the first day of dosing), 14 days of dosing, and a follow-up period of approximately 3 weeks.

8.9. **Prohibitions and Restrictions**

8.9.1. **Prior and Concomitant Medications**

All prescription and over-the-counter medications, dietary supplements (including vitamins), and herbal supplements taken by the subject during the 30 days before screening will be recorded on the Prior and Concomitant Medications page of the eCRF.

Subjects must be on a stable regimen of steroidal treatment for CAH for a minimum of 30 days before PD baseline (Day -7) and the regimen should remain stable throughout the study.

subjects of childbearing potential may use hormonal contraception during the study if taken for at least 3 months prior to screening. Subjects who are on stable medication regimens to treat stable medical conditions (other than CAH) are allowed to participate in the study.

The following medications are prohibited from 30 days before screening until the final study visit (or early termination):

Orally administered glucocorticoids for indications other than CAH.

10 May 2019 Confidential 39 • As-needed doses of anxiolytics.

Any concomitant medication taken during the study will be recorded on the Prior and Concomitant Medications page of the eCRF with indication, total daily dose, route, and dates of drug administration.

Any additions, deletions, or changes in the dose of medications during the study should be recorded on the appropriate eCRF page.

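### Day 7 is the only scheduled morning PD draw with no visible hold on the usual morning steroid, yet it is compared with a steroid-held baseline

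*Protocol*

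**What the plan says.** **Day 7.** Protocol 8.7.3.2 collects blood for "PD biomarkers at approximately 12 hours (±2 hour window) after the Day 6 evening dose and prior to the Day 7 morning dose". Protocol 8.4 and Table 2 footnote i show which dose is meant: "study drug dosing should not occur until after the blood sample has been collected". The visit is outpatient.

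**The other scheduled morning PD draws** each carry a steroid rule:
- Screening (Table 2 footnote i): "Screening (between 0700 and 1000 hours; must be collected prior to first morning dose of hydrocortisone".
- Day -6 (Protocol 8.7.2): "Subjects will not take their usual morning dose of steroidal treatment until after the 1000 hours PD sample is collected on Day -6".
- Day 2 (Protocol 8.7.3.1): the "usual morning dose of concurrent steroidal treatments, study drug dosing, and breakfast (snacks will be allowed prior to breakfast) will be delayed" until the 15-hour sample has been taken, at about 1000.
- Day 15 (Protocol 8.7.3.3): the "usual morning dose of concurrent steroidal treatments will be administered after the 15 hour postdose PD samples are collected", again at about 1000.

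**Instructions before Day 7.** The Day 2 discharge list covers study drug, meals, diary, contraception, AEs and new concomitant medication. The reminder call (Table 2 footnote o) asks sites to check compliance and diary completion and to "remind them to bring subject study diary and remaining study drug to the Day 7 visit". Neither mentions steroid timing. Protocol 8.9.1 asks that the steroid regimen stay stable.

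**Analysis.** SAP 9.1 summarises PD values for each parameter, visit and timepoint, with change from the PD baseline value at the same timepoint. It drops Day 7 and Day 21 only from the 24-hour averages. Protocol 12.7 also uses timepoint-matched baseline changes, with no exception for Day 7. SAP 9.2 averages the 12- and 15-hour values at each visit, or uses one if only one is available, and reports changes to Day 1 and Day 14 only.

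**The concern.** On the three inpatient mornings, staff control when the steroid is taken. On Day 7 the subject comes from home. Taking the usual steroid before travelling, and study drug after the draw, breaks no visible rule.

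Protocol 4.1 describes glucocorticoids as the treatment used to bring down ACTH and androgen excess. A dose taken before the draw could therefore lower ACTH, 17-OHP, androstenedione and testosterone against a baseline sample taken without it. With no control arm, that fall would look like drug effect. Oral hydrocortisone could move measured cortisol the other way, upwards.

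Day 7 is the only scheduled PD sample between Day 2 and Day 14, so its row is what a reader would use to judge how early the response appears. The visible data collection does not clearly allow a later correction. Concomitant medication is recorded "with indication, total daily dose, route, and dates of drug administration" (Protocol 8.9.1), which includes no clock time. The diary covers study drug, and the dosing-time sentence in Protocol 9.6 sits under study drug compliance.

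**Working it through.** The plan has no figure to reproduce, so the check sets the rules side by side and works out the clock times.

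**1. Draw times.** Evening dosing on Days 3 to 13 is at about 1900 (Protocol 9.3 and Table 2).
- Day 7 draw: 1900 + 12 h = 0700; with ±2 h, 0500 to 0900.
- Day 21 draw: Day 14 at 1900 + 168 h = Day 21 at 1900. The window of -8 h/+3 days runs from Day 21 at 1100 to Day 24 at 1900. By schedule this is an evening draw.

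**2. Steroid rule at each scheduled morning PD occasion** (samples counted in the SAP 9.2 window, 0700 to 1000)

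| Occasion | Setting | Samples | Steroid held? |
|---|---|---|---|
| Screening | outpatient | 1 | yes |
| Day -6 (0700, 1000) | inpatient | 2 | yes |
| Day 2 (12 h, 15 h) | inpatient | 2 | yes |
| Day 7 (12 h) | outpatient | 1 | none visible |
| Day 15 (12 h, 15 h) | inpatient | 2 | yes |

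The hold is present at 4 of 5 occasions and at 7 of 8 samples. Protocol 12.7 treats 0300 and 0700 as the morning 17-OHP times. Adding the three 0300 samples (Days -6, 2 and 15) gives 10 of 11. Either way Day 7 is the one exception. On treatment it is 1 of 3 mornings (Days 2, 7 and 15).

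**3. What Day 7 is compared with.** The baseline value matching the 12-hour timepoint is Day -6 at 0700, inside the hold that lasts until after the 1000 sample.

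**4. Which outputs use Day 7**

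| Output | Uses Day 7? |
|---|---|
| SAP 9.1 observed and change rows, and figures (5 biomarkers) | yes, by general wording |
| SAP 9.1 24-hour averages | no, excluded |
| SAP 9.2 observed morning-window values (4 biomarkers) | possibly |
| SAP 9.2 changes, percent changes and waterfall plots | no, Day 1 and Day 14 only |
| SAP 9.3 responders | no, baseline and Day 14 |
| SAP 9.4 PD/PK plots | no, Day 14 |
| PK | not affected by steroid timing relative to the PD draw |

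**5. Size.** The documents give neither the usual steroid clock time nor the effect of a single dose within hours, so the bias cannot be derived. Its form can be shown under assumptions. Suppose k of 12 subjects take the steroid before the draw and it lowers 17-OHP by a fraction r of baseline, with baseline similar across subjects. The spurious mean fall, as a fraction of baseline, is

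(k/12) × r

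This is zero if k = 0 or r = 0. For r from 10% to 50%:
- k = 3: 0.25 × r = 2.5% to 12.5%
- k = 6: 0.50 × r = 5% to 25%
- k = 12: 1.00 × r = 10% to 50%

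Both k and r are invented for illustration. Other analytes may respond differently, and for cortisol the sign may reverse.

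**The case against.** **The consequence is minor.** The PD results the SAP develops most (morning-window changes, responders, PD/PK plots) all rest on steroid-held visits. The PD analysis set requires a Day 1 or Day 14 value, and the study is descriptive with about 12 subjects. This stands and limits the point to low severity. A reader might infer that the responder rates or Day 14 changes are biased; the documents do not support that.

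**The SAP link is partly inference.** SAP 9.1 does not name Day 7 in its change sentence and speaks of postdose values, while Protocol Table 1 labels the Day 7 draw as predose. However, the sample is defined as 12 hours after an evening dose, and SAP 9.1 excludes Day 7 only from the 24-hour averages, so inclusion is the natural reading. SAP 9.2 is weaker: its single-value rule reads like a missing-data rule, and Day 7 has no scheduled 15-hour draw. The text permits a Day 7 morning-window value but does not call for one.

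**Redaction.** Inclusion criterion 7 and Protocol 8.9.1 have gaps where steroid rules are set out, and the consent and assent forms are not available. The Day 7 procedure list and the PD footnote read as complete, but a hold elsewhere cannot be ruled out.

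**The difference may be deliberate.** Draws late in the Day 21 window, on the mornings of Days 22 to 24, also lack a steroid rule, so it would be too strong to say that every other possible morning draw is held. But Day 21 is an evening draw by schedule, and screening shows that an outpatient hold is workable. No reason for treating Day 7 differently is given.

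**Pre-draw dosing might be detectable.** Cortisol is measured in the same Day 7 sample, and screening cortisol must be below 5 µg/dL, so a raised value could reveal recent hydrocortisone. This stands in part: it would not necessarily reveal prednisone or dexamethasone, both of which SAP 8.3 anticipates.

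**Conclusion.** The concern holds in a narrow form, at low severity. In the visible text Day 7 is the only scheduled morning PD draw without a steroid hold, and its 12-hour value is set against a baseline sample taken with the steroid held. The exposure is the Day 7 observed and change rows and figures in SAP 9.1, and possibly one Day 7 observed value per biomarker in SAP 9.2.

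This rests on three assumptions: that no redacted passage or participant form contains a hold, that SAP 9.1's general wording covers Day 7, and that some subjects take their steroid before the draw. Direction can be argued from Protocol 4.1; size cannot. A reader might take the percentages above as an estimate of bias, but they only restate the assumed k and r.

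**What to change.** **Protocol.** In 8.7.3.2, 8.4, Table 2 footnote i and the synopsis, state that the Day 7 PD sample is taken before the usual morning steroid as well as before study drug. The steroid follows right after the draw. Study drug is then taken with breakfast, as 8.7.3.2 (dosing at home) and 9.3 (dosing with a meal) already require. Add the instruction to the Day 2 discharge list and the reminder call. Record the clock time of the last steroid dose before the Day 7 draw.

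**SAP 9.1.** Flag Day 7 samples drawn after the morning steroid and show the Day 7 summary with and without them. If times were not collected, footnote Day 7 as not steroid-controlled, with Day 7 cortisol as a partial check in hydrocortisone users.

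**SAP 9.2.** State that Day 7 is excluded from the morning-window summary.

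**Cost.** One clause in four protocol places, one line in the discharge list and one in the reminder call, one eCRF time field, and short additions to SAP 9.1 and 9.2. Subjects face a short steroid delay, to 0900 at the latest on the nominal schedule, against the 1000 delay already required on Days -6, 2 and 15. If Day 7 sampling is already complete, only the SAP changes apply.

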8.7.4. Follow-Up Period

Follow-up visits will be conducted on Days 17 and 21 with a final study visit on Day 35 (or early termination). Based on their preference, the subject will either come into the study center, or the qualified home healthcare provider will come to the subject's home on Days 17 and 21. The final study visit will be conducted at the study center.

8.7.4.1. Follow-Up Visits: Days 17 and 21

The following procedures will be performed on Days 17 and 21 (-8 hours/+3 days):

- Collect blood sample for PD biomarkers at approximately 168 hours (-8 hours/+3 days; Day 21 only) following the last dose.
- Collect blood samples for PK at approximately 72 hours (-8 hours/+3 days) and 168 hours (-8 hours/+3 days) following the last dose.
- AE monitoring.
- Record concomitant medications.

At each visit, subjects will be reminded to notify the investigator or study staff by telephone if they experience any AEs and before taking any concomitant medications.

At the Day 21 visit, subjects will be reminded to report to the study center on Day 35 (+7 days) for the final study visit (or at early termination).

